## **7.3 Pregnancy**

Pregnancy should be considered a serious adverse event in the case when a subject is found to be pregnant while taking dupilumab.

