### **1.3.2 Human Pharmacokinetics of Dupilumab**

#### **Absorption**

Following an initial subcutaneous (SC) dose of 600 mg, dupilumab reached peak mean  $\pm$ SD concentrations (Cmax) of 70.1 $\pm$ 24.1 mcg/mL by approximately 1 week post dose.

Steady-state concentrations were achieved by Week 16 following the administration of 600 mg starting dose and 300 mg dose either weekly (twice the recommended dosing frequency) or every other week. Across clinical trials, the mean  $\pm$ SD steady-state trough concentrations ranged from 73.3 $\pm$ 40.0 mcg/mL to 79.9 $\pm$ 41.4 mcg/mL for 300 mg administered every 2 weeks and from 173 $\pm$ 75.9 mcg/mL to 193 $\pm$ 77.0 mcg/mL for 300 mg administered weekly. The bioavailability of dupilumab following a SC dose is estimated to be 64%. Distribution The estimated total volume of distribution was approximately 4.8 $\pm$ 1.3 L.

**Elimination** The metabolic pathway of dupilumab has not been characterized. As a human monoclonal IgG4 antibody, dupilumab is expected to be degraded into small peptides and amino acids via catabolic pathways in the same manner as endogenous IgG. After the last steady-state dose of 300 mg Q2W or 300 mg QW dupilumab, the median times to non-detectable concentration (<78 ng/mL) are 10 and 13 weeks, respectively.

**Dose Linearity** Dupilumab exhibited nonlinear target-mediated pharmacokinetics with exposures increasing in a greater than dose-proportional manner. The systemic exposure increased by 30-fold when the dose increased 8-fold following a single dose of dupilumab from 75 mg to 600 mg (i.e., 0.25times to 2-times the recommended dose). **Weight** Dupilumab trough concentrations were lower in subjects with higher body weight. **Immunogenicity** Development of antibodies to dupilumab was associated with lower serum dupilumab concentrations. A few subjects who had high antibody titers also had no detectable serum dupilumab concentrations.

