### **4.2.2 Exclusion Criteria**

Any of the following exclusion criteria would prohibit patient participation in the study:

1. Prior dupilumab use
2. Treatment with a systemic immune-regulating medication within 3 months of the baseline visit or the patient's prior patch testing, whichever is longer. Examples of these medications include azathioprine, methotrexate, mycophenolate mofetil, Janus kinase inhibitors, and phototherapy (including tanning booths). Cyclosporine or prednisone may not have been used within 1 month of the baseline visit.
3. Treatment with other biologic agents, such as TNF inhibitors, anti-IL 17 agents, anti-IL 12/23 agents, or anti-IL 23 agents, within 4 months of baseline visit or the patient's prior patch testing, whichever is longer.

4. Use of rituximab within at 6 months (or until lymphocyte counts have normalized if longer than 6 months) of the baseline visit or the patient's prior patch testing, whichever is longer.
5. Treatment with topical corticosteroids, topical phosphodiesterase inhibitors or topical calcineurin inhibitors within 1 week before the baseline visit
6. Other active conditions, such as psoriasis, that may confound clinical evaluations of dermatitis and patient-reported symptoms.
7. Increased risk of infection or reactivated infection, including history of human immunodeficiency virus, hepatitis B, hepatitis C, endoparasitic infections, receipt of a live attenuated vaccine within 3 months of the baseline visit, chronic or acute infection requiring treatment within 4 weeks of the baseline visit, immunosuppressed status (ie recurrent or resistant opportunistic infections)
8. Malignancy within 5 years of the screening visit excluding local cutaneous squamous cell carcinoma, basal cell carcinoma or cervical carcinoma in situ that has been fully treated.
9. Women who are or plan to become pregnant or breastfeed during study participation or are unable or not willing to use birth control during the study and for 4 months after the last dose of dupilumab. Options for birth control include abstinence, double barrier (ie male condom and female diaphragm), vasectomy, intrauterine device, and hormonal contraception. Females who have not had menses within 1 year of the baseline, bilateral tubal ligation, hysterectomy, and/or bilateral oophorectomy visit do not require additional methods contraception during study participation.

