# **6 STUDY ASSESSMENTS AND PROCEDURES**

## **6.1 Time and Events Schedule**

Time and events schedule is detailed in the table below:

Visit Number	1 Screening	2 Week 0	3 Week 0 +72-120 Hours	4 Week 6	5 12 Weeks	6 12 Weeks +72-120 hours	7 Early Termination /Unscheduled Visit
---------------------	------------------------	-------------------------	---	-------------------------	---------------------------	---	---

Day (+/- 3 days)	-34 to 0	1	4	42	84	87	N/A
Informed eConsent	X						
Inclusion/Exclusion Criteria	X						
Medical History	X						
Prior/Concurrent Medications	X						X
Safety Assessments							
Adverse Events		X	X	X	X	X	X
Clinical Efficacy Assessments							
Patch Test Site Reaction			X			X	
IGA	X	X		X	X		X
EASI		X		X	X		X
BSA		X		X	X		X
Patient-Reported Outcomes							
DLQI		X		X	X		X
NRS Itch		X		X			X
SLEEPYQ		X		X	X		X
Distribute Diaries (Allergen Avoidance and Dupilumab Dosing)		X					
Collect Diaries (Allergen Avoidance and Dupilumab Dosing)						X	X
Laboratory Assessments							
Pregnancy Test	X	X		X	X		X
Biomarker Skin Sample			X			X*	
Biomarker Serum Sample		X	X		X	X	
Medication Dosing							
In-Office Dosing			X				
Dispense Study Medication			X	X			
Patch Testing							
Patch Test Material Placement		X			X		
Patch Test Material Removal							
Photographs							
Patch Test Site Photographs		X	X		X	X	
Dermatitis Photographs			X			X	X

\*In addition to the allergen patch site and normal skin, an additional biopsy will be done on an area of persistent dermatitis if present unless in an anatomic location not amenable to biopsy (face, hands, elbows, knees, genitals, feet).

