#### **7.1.1 Serious Adverse Events**

A serious adverse event may include those that result in death, life-threatening events, inpatient hospitalization or prolonged hospitalization, disability/incapacity, congenital anomaly/birth defect, important medical event, suspected transmission of an infectious agent through the study drug, and the case of the current study pregnancy.

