### **7.2.1 Serious Adverse Event Collecting and Reporting**

Serious adverse event collection should begin at the time that informed consent is obtained. All serious adverse events must be collected and reported, including those that occur within 30 days after the final dupilumab dose. If a serious adverse event occurs after this period, but is related to dupilumab or procedures performed in the study these should also be reported. If there is uncertainty whether an event is a serious one, a serious adverse event report should be completed. All serious adverse events, whether related or not related to dupilumab, must be reported to Regeneron within 24 hours.

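### Sections 7.1.1 and 7.3 define pregnancy as a serious adverse event differently, and from day 30 to about day 120 after the last dose a pregnancy is reportable only if judged related

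*Combined protocol and SAP*

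**What the plan says.** Two sections classify pregnancy as an SAE. Section 7.1.1 ends its list of SAEs with "and the case of the current study pregnancy" and attaches no time limit. Section 7.3, the section devoted to the subject, says: "Pregnancy should be considered a serious adverse event in the case when a subject is found to be pregnant while taking dupilumab".

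Section 7.2.1 sets the reporting rules. Collection starts at consent, and "All serious adverse events must be collected and reported, including those that occur within 30 days after the final dupilumab dose". After that the rule becomes conditional: "If a serious adverse event occurs after this period, but is related to dupilumab or procedures performed in the study these should also be reported". Where it is unclear whether an event is serious, an SAE report is to be completed. Every SAE goes to the drug's supplier within 24 hours.

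Exclusion criterion 9 (section 4.2.2 Exclusion Criteria, repeated in the synopsis) requires birth control "during the study and for 4 months after the last dose of dupilumab". Sections 4.1 and 5.3 place the last dose, and the end of the treatment portion, at Week 10 +72-120 hours. The "Pregnancy Test" row of the Time and Events Schedule (section 6.1) has entries at screening, Week 0, Week 6, Week 12 and early termination. Section 4.1 ends participation at Week 12 +72-120 hours.

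**The concern.** Site staff with a positive test will naturally turn to 7.3, and its condition is narrower than the entry in 7.1.1. It also depends on when the pregnancy is found, not on when conception occurred, so a pregnancy that began during dosing but came to light afterwards is not clearly within it. Nothing says which section governs.

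The larger matter is the stretch after the 30-day window. By requiring contraception for 4 months, the protocol treats pregnancy in that period as something to avoid because of exposure, yet its reporting rules do not reach that far without a relatedness judgement. At stake is the completeness of the record of exposed pregnancies and their outcomes. No efficacy endpoint, sample size or analysis is affected.

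**Working it through.** The plan gives no figure to reproduce. The check is a comparison of the rules plus date arithmetic.

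**1. Rules side by side**

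| Source | What it does | Reach after the last dose |
|---|---|---|
| 7.3 | Pregnancy is an SAE if found while on drug | Not stated; depends on what counts as taking the drug |
| 7.1.1 | Pregnancy is an SAE | No limit of its own |
| 7.2.1 | SAEs collected and reported | 30 days unconditionally; later only if related |
| Criterion 9 | Contraception required | 4 months |

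Only the first two rows classify pregnancy, and they differ. Criterion 9 is an eligibility and contraception rule, not a reporting window.

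**2. Last dose.** Two syringes at Week 0 +72-120 hours and one each at Weeks 2, 4, 6, 8 and 10 give 2 + 5 = 7, which matches the 7 doses over 10 weeks in the synopsis. In elapsed days the last dose is at 70 + 3 = 73 to 70 + 5 = 75.

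**3. Week 12 test.** Week 12 is day 84.
- Elapsed days: 84 − 75 = 9 to 84 − 73 = 11 days after the last dose.
- The schedule's own numbering (Week 0 = Day 1, first dose Day 4 to 6, last dose Day 74 to 76): 84 − 76 = 8 to 84 − 74 = 10 days.
- With the ±3-day visit window, over both conventions: 8 − 3 = 5 to 11 + 3 = 14 days.

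The test therefore comes after the stated end of treatment, but no later than one 2-week dosing interval after the last dose and well inside the 30-day window.

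**4. Days without an unconditional rule.** Four months is about 120 to 123 days. Subtracting the 30-day window leaves 120 − 30 = 90 to 123 − 30 = 93 days. Unconditional reporting covers at most 30/120 = 25% of the contraception period after the last dose.

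**5. What happens in those days.** The final visit, at Week 12 +72-120 hours, is (84 + 3) − 75 = 12 to (84 + 5) − 73 = 16 days after the last dose. The schedule shows nothing later. A pregnancy that does come to light must be reported only if related, and section 7.1.3 defines related as a reasonable causal relationship between giving the drug and the event. Conception itself would rarely be judged to be caused by the drug, so a pregnancy that matters because of exposure would usually fail that test.

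**6. Outcome.** Section 7.1.1 lists congenital anomaly and birth defect as SAEs. For a pregnancy first found at Week 12 or later, the birth would fall well after both the 30-day window and the end of participation. No section requires follow-up to that point. The instruction in 7.2.2 to monitor events until they resolve or stabilise is written for non-serious events.

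**7. Drug persistence (supporting only).** Section 1.3.2 states that after the last steady-state dose, every 2 weeks or weekly, "the median times to non-detectable concentration (<78 ng/mL) are 10 and 13 weeks, respectively". For the 2-weekly schedule that is 10 × 7 = 70 days, or 40 days past the 30-day window. Dosing here stops before the Week 16 steady state described in the same section, so the time may be shorter. The argument does not need this figure.

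**The case against.** A reader might infer that pregnancy is an SAE only while a subject is dosing, that a positive Week 12 test escapes the rules, and that the trial could therefore report no pregnancies despite such a test. The documents do not support this. Section 7.3 does not say that pregnancy is otherwise not an SAE, and 7.1.1 lists it without limit. A test 9 to 11 days after the last dose lies inside the 30-day window, and any doubt about seriousness is met by the instruction in 7.2.1 to file a report. A subject still within 14 days of a 2-weekly dose may also fairly be described as taking the drug. The inference needs 7.3 to be read in isolation.

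It can also be said that a contraception period longer than an SAE window is a difference in scope, not a contradiction. That is right, and criterion 9 should not be counted as a third definition. Related SAEs remain reportable after 30 days. Subjects may also be told in the consent form to report a later pregnancy; those pages were not available for review.

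The synopsis mentions follow-up 3 months after an undefined FV. Beside the first-visit dates on the same line, it reads most naturally as 3 months from first visit, which fits the 12-week schedule. Section 4.1 and the schedule show no later contact.

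None of this reconciles 7.1.1 with 7.3. Nor does it supply an unconditional reporting rule between day 30 and about day 120, or follow-up to outcome.

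**Conclusion.** The point holds in two parts. First, 7.1.1 and 7.3 give different scopes for pregnancy as an SAE and must be reconciled; the practical risk is that a site applies 7.3 alone. Second, for about 90 to 93 of the 120 to 123 days of contraception after the last dose, reporting depends on a relatedness judgement that does not suit pregnancy, no contact is scheduled, and follow-up to outcome is not required.

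The size in subjects cannot be stated. The number of women of child-bearing potential among at most 30 is not given, and no pregnancy rate is given. The conclusion assumes that the 4 months run from the Week 10 dose and that no unseen consent text closes the gap. It is a cheap improvement to safety capture. The Week 12 test is not lost under the rules as a whole.

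**What to change.** Make 7.1.1, 7.2.1 and 7.3 say the same thing: any pregnancy in a subject that comes to light from the first dose through the 4-month period already named in criterion 9 is reported within 24 hours regardless of relatedness, and is followed to outcome. This should not shorten the collection of SAEs from consent that 7.2.1 already sets. At the last visit, tell women of child-bearing potential to report a pregnancy in that period, and check that the consent form says so.

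One remote contact at the end of the period is optional. Ability to use Zoom is already an entry condition, so it needs no new arrangement.

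The cost is protocol and, if needed, consent wording. The downside is that safety follow-up for this one item stays open about 4 months after the last dose, and longer for any pregnancy being followed, in a subset of at most 30 subjects. Treatment, visits, endpoints and analyses are unchanged.

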## **8 DATA MONITORING COMMITTEE**

Not applicable.

## **9 STATISTICAL CONSIDERATIONS**

### **9.1 Sample Size Determination**

Open label, pilot design: Descriptive statistics to report baseline subject characteristics. A sample size of 11 participants achieves 80% power to detect a mean change of -1.0 (i.e., one less reaction on average) with an estimated standard deviation of 1.0 using a two-sided Wilcoxon test with significance level

$\alpha=0.05$  and assuming the actual distribution of change is normal. Upweighting of 10-25% would add conservatively to our ability to detect a change and is reflected in the final sample size estimation of 14 subjects. Therefore, we need a minimum of 14 subjects who complete the study to have enough statistical power. In order to accomplish this, we will aim to enroll a maximum of 30 subjects.

## **9.2 Populations for Analyses**

Study population will be subjects ages 18 years and older of any race/ethnicity and gender, with clinically diagnosed allergic contact dermatitis who have not improved following allergen avoidance and topical therapies within 6 months of patch testing.

## **9.3 Endpoint Definitions**

Investigator's Global Assessment (IGA) score

The investigator's global assessment is a physician-reported global assessment of disease activity (range 0-4) with 0 being clear and 4 being severe.

Body Surface Area (BSA)

The body surface area is a physician-reported measure of the amount of disease involvement. The patient's palm size approximates 1% of body surface area involvement.

Eczema Area and Severity Index (EASI) score

The eczema-area-and-severity-index score is a composite score of disease severity and extent of disease distribution. It was initially developed for evaluation of eczema. Disease severity (range 0-3; 0 being no disease and 3 being severe disease) is a measure of redness, thickness/induration, scratching, and lichenification. Each characterization is measured separately for body regions (head and neck, trunk, upper extremities, and lower extremities) to calculate a regional score. The total score is a sum of the four body regions (range 0-72).

Numerical Rating Scale (NRS) itch

The numerical rating scale for itch is a patient-reported measure of itch (range 0-10) with 0 being no itch and 10 being the worst imaginable itch.

Dermatology Life Quality Index (DLQI)

The Dermatology Life Quality Index is a 10-question, patient-reported instrument to assess impact of skin diseases on patient quality of life.

## SLEEPY-Q

The Sleepy-Q is a patient-reported questionnaire that consists of 18 questions. It assesses three dimensions of sleep in patients with inflammatory skin conditions: sleep disturbance, causes of sleep disturbance and impairment related to sleep disturbance.

## **9.4 Analyses**

### **9.4.1 Demographics and Baseline Characteristics**

Demographics and baseline disease characteristics including age, gender, ethnicity, age of onset of allergic contact dermatitis, body areas of dermatitis involvement, prior treatments for allergic contact dermatitis (including prescription therapies and prior recommended allergen avoidance strategies) will be documented at the initial screening visit.

### **9.4.2 Safety Analyses**

Subjects will be questioned about experiencing any adverse events at every follow-up visit.

### **9.4.3 Efficacy Analyses**

At the time of enrollment, clinical parameters will be measured and recorded including their prior positive patch test reactions type and strength, IGA, EASI, BSA, DLQI, NRS itch, and SLEEPYQ. Patients will also be provided with a diary to record their allergen avoidance strategies and dupilumab dosing. A sample of blood will also be taken. At the week 0 +72-120 hours study visit their patch test site reaction will be recorded. Samples of skin will be placed on sterile, saline soaked gauze and transported back to the [name] laboratory at [name]. One portion of the skin will be embedded in OCT and frozen at -20°C for future cryosectioning and the second portion of the skin will be placed in culture for the isolation of skin T cells. T cells and dendritic cells will then be analyzed by molecular and cellular techniques including TCR sequencing, nanostring, and multiplex fluorescence. A second sample of blood will also be taken. DNA will be extracted from blood samples and TCR sequencing will be done through collaborators at Adaptive as a fee for service arrangement. Isolated DNA from biopsies and blood samples will be sent, these will be coded with no identifiable information shared. Any leftover samples may be stored for future projects if a subject provides this optional consent.

The primary clinical efficacy endpoint will be the number of patients who achieve a reduction in patch test site reactions from 2+-3+ at baseline to "?" or no reaction at week 12 +72-120 hours. Secondary endpoints will include number of patients who achieve a reduction in investigator global assessment (IGA) from 3 or greater at screen and baseline to 0 or 1 at Week 6, and Week 12; quantification of the inflammatory markers (Th1, Th2, Th17, Th22 immune pathways) in the blood and skin of patients before and after dupilumab; changes in IGA from baseline to week 12. Other secondary endpoints: Change in baseline eczema-area-and-severity-index (EASI), body surface area (BSA), numerical rating scale (NRS) itch, dermatology life quality index (DLQI), and SLEEPYQ from baseline to Week 6 and Week 12; changes in IGA from baseline to Week 6 and Week 12; changes in baseline eczema-area-and-severity-index (EASI), body surface area (BSA), numerical rating scale (NRS) itch, dermatology life quality index (DLQI), and SLEEPYQ from baseline to Week 6 and Week 12; identification and quantification of the most prevalent T cell clones in the skin before therapy and how those clones change after therapy using high-throughput sequencing of the TCRB gene.

## **10 STUDY MANAGEMENT**

### **10.1 Compliance with the Protocol**

#### **10.1.1 Compliance with the Protocol and Protocol Revisions**

Study procedures are performed according the protocol, approved by the IRB. Signed approval by the IRB should be sent to the study sponsor. If there is an immediate hazard to study subjects, deviation or change in the protocol may be made prior to IRB approval. The deviation or change should be submitted as soon as possible to the IRB for review, the study sponsor, and any regulatory authorities as required by local regulations.

If there is a study amendment that significantly changes the study design and/or potential subject risk, the informed consent form must be revised and approved by the IRB, informed consent must be obtained from all subjects in the study for those affected by the amendment and who agree to continue their participation, and used for all new subjects.

## **10.2 Records Retention**

### **10.2.1 Records Retention**

All study documents will be retained for the maximum period required by applicable regulations/guidelines or institution procedures, whichever is longer.

### **10.2.2 Study Drug Records**

The research pharmacy will maintain a record of dupilumab study drug.

## 11 LIST OF ABBREVIATIONS

ACD	Allergic Contact Dermatitis
BSA	Body Surface Area
GCP	Good Clinical Practice
CTCAE	Common Terminology Criteria for Adverse Events
DLQI	Dermatology Quality of Life Index
EASI	Eczema Area and Severity Index
HTS	High Throughput Sequencing
ICH	International Conference on Harmonization
IGA	Investigator's Global Assessment
IRB	Internal Review Board
NRS	Numerical Rating System
TNF	Tumor Necrosis Factor

